6.2 IMPORTANT PROTOCOL DEVIATIONS

Data discrepancies and deviations from the CTP will be identified for all treated subjects. Consistency check listings (for identification of deviations of time windows) and a list of protocol deviations (e.g. deviations in drug administration, in blood sampling times, etc.) will be provided to be discussed prior to Data base lock (DBL). All manual deviations identified at the sites by the CRAs and deviations too complex to program will be reviewed by the trial team to decide which are considered important. For definition of important protocol deviations (iPD), and for the process of identification of these, refer to the Boehringer Ingelheim (BI) SOP "Identify and Manage Important Protocol Deviations (iPD)" (2).

Important protocol deviation (iPD) categories are pre-specified in the iPD specification file (DV domain) (3). IPDs will be identified no later than DBL, and the iPD categories will be updated as needed.

If any iPDs are identified, they are to be summarised into categories and will be captured in the iPD specification file (DV domain) (3) and in the decision log (4). Both documents will be stored within the TMF in EDMS.

The iPDs will be summarized and listed in the CTR.

6.3 INTERCURRENT EVENTS

This section is not applicable.

6.4 SUBJECT SETS ANALYSED

Section 7.2.1.1 of the CTP:

[figure not shown]
Statistical analyses will be based on the following analysis sets:

- *Treated set (TS): The treated set includes all subjects who were treated with at least one dose of trial drug. The treated set will be used for safety analyses.*

The study was prematurely terminated after run-in period. No PK parameter values were assessed. Therefore, the pharmacokinetic parameter analysis set as defined in the CTP is not applicable.

An additional analysis set will be defined for listings of disposition:

- *Entered set (ES): The entered set includes all subjects who were entered to the trial.*

6.6 HANDLING OF MISSING DATA AND OUTLIERS

Handling of missing data and outliers will be performed as described in the CTP, Section 7.3: Missing or incomplete AE dates are imputed according to BI standards (see BI-KMED-BDS-HTG-0035) (5).

6.7 BASELINE, TIME WINDOWS AND CALCULATED VISITS

Baseline is defined as the last measurement before first administration of COC.

Section 6.1 of the CTP:

Exact times of measurements outside the permitted time windows will be documented. The acceptable time windows for screening and the end of trial examination are provided in the CTP Flow Chart.

Study measurements and assessments scheduled to occur 'before' trial medication administration are to be performed and completed within a 2 h-period prior to the trial drug administration.

If not stated otherwise in the CTP Flow Chart, the acceptable deviation from the scheduled time for vital signs, ECG, and laboratory tests will be ± 30 min.

If scheduled in the CTP Flow Chart at the same time as a meal, blood sampling, vital signs, and 12-lead ECG recordings have to be done first. Furthermore, if several measurements including venipuncture are scheduled for the same time, venipuncture should be the last of the measurements due to its inconvenience to the subject and possible influence on physiological parameters.

During the run-in period, administration of Yasmin® tablets must be done by the subjects at home. The subjects are advised to take Yasmin® tablets with a cup of water at the same time each day, approximately between 06.00 and 10.00 am local time.

Adherence to time windows will be checked via the consistency check listings prior to DBL.

Unscheduled measurements of laboratory data and vital signs data will be assumed to be repeat measurements of the most recent scheduled measurement (e.g. for follow-up or confirmation of a particular value). Therefore, unscheduled measurements will be assigned to the planned time point of the previous scheduled measurement.

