# FLOW CHART

Period	Visit	Day	Planned time (relative to first drug administration) [h:min]	Approximate clock time of actual day [h:min]	Event and comment	Safety laboratory	PK plasma, BI 1358894	PK plasma, COC	Exploratory PD serum 	12-lead ECG	Vital signs (BP, PR)	Suicidality Assessment 	Questioning for AEs and concomitant therapy 
SCR	1	-91 to -			Screening (SCR) 	$A^6$				X	X	X	
Run	2	-56 to -			Self-administration of COC	x 							Х
-in 		-7 to -1			Follow up call (COC free interval)								х
	3	1	0:00	08:00	Dosing COC 	$\mathbf{B}^{8}$		x 	x 				X
		2	24:00	08:00	Dosing COC 								X
		3	48:00	08:00	Dosing COC 								X
		4	72:00	08:00	Dosing COC 								X
		5	96:00	08:00	Dosing COC 								X
		6	120:00	08:00	Dosing COC 								X
		7	144:00	08:00	Dosing COC 								X
		8	168:00	08:00	Dosing COC 								X
		9	192:00	08:00	Dosing COC 								X
		10	216:00	08:00	Dosing COC 	x 							X
		11	240:00	08:00	Dosing COC 								X
		12	264:00	08:00	Dosing COC 								Х
		13	288:00	08:00	Dosing COC 								X
		14	312:00	08:00	Dosing COC 								X
-		15	336:00	08:00	Dosing COC 								X
Period 1		16	360:00	08:00	Dosing COC 								X
Per		17	384:00	08:00	Dosing COC 								X
		18	408:00	08:00									X
		19	432:00	08:00	Dosing COC 								X
		20	456:00	08:00	Dosing COC 								X
			466:00	18:00	Admission to trial site	x 					X		X
		21	479:30	07:30	Start of continental breakfast								X
			480:00	08:00	Dosing COC 			x 	x 				X
			480:30	08:30				X					X
			481:00	09:00				X					X
			481:30	09:30				X					X
			482:00	10:00	240 mL fluid intake			X					X
			482:30	10:30				X					X
			483:00	11:00		-		X					X
			483:30	11:30	040 7 0 11 1 7 12			X					X
			484:00	12:00	240 mL fluid intake, Lunch 			X					X

c41232811-04 Trial Protocol

Page 5 of 84

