- 7. The intake of Yasmin® starts depending on the subjects' actual menstruation cycle and at least -28 days before Day 1 of first treatment period. In the run-in period, the subjects will take one tablet of COC daily until Day -8. On Day 7 to Day -1 no COC tablets will be given in order to induce withdrawal bleeding. Self-administration in the morning with no requirement of fasting. Self-administration to be documented in the diary. A negative urine pregnancy test should be performed at the site 1 to 7 days before start of the run-in. Details are outlined in Section 4.1.4
- 8. Urine pregnancy test. Additional urine drug screening on day 20 of each period.
- 9. Blood collection takes place within 10 minutes before dosing.
- 10. Suicidality assessment using the Columbia-Suicidal Severity Rating Scale (C-SSRS): 'Screening/Baseline' version at Visit 1, and 'since last visit' version at other visits.
- 11. Measurement of exploratory pharmacodynamic parameters: estradiol, luteinizing hormone (LH), follicle stimulating hormone (FSH), and progesterone. The samples will be taken in duplicate.
- 12. Dosing at the trial site after a continental breakfast (for details see Section 4.1.4).

c41232811-04 Trial Protocol

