c41232811-04 Trial Protocol

Page 44 of 84

Proprietary confidential information © 2023 Boehringer Ingelheim International GmbH or one or more of its affiliated companies

Table 5.2.3: 1 Routine laboratory tests (cont.)

Functional lab group	BI test name [comment/abbreviation]	A	В	С
Substrates	Glucose (Plasma)	X	X	X
	Creatinine	X	X	X
	GFR/ CKD-EPI	X		
	Bilirubin, Total	X	X	X
	Bilirubin, Direct	X	X	X
	Protein, Total	X	X	X
	C-Reactive Protein (Quant)	X	X	X
	Uric Acid	X		
	Cholesterol, total	X		
	Cholesterol, HDL	X		
	Cholesterol, LDL	X		
	Triglyceride	X		
Electrolytes	Sodium	X	X	X
	Potassium	X	X	X
Urinalysis (Stix)	Urine Nitrite (qual)	X		X
	Urine Protein (qual)	X		X
	Urine Glucose (qual)	X		X
	Urine Ketone (qual)	X		X
	Urobilinogen (qual)	X		X
	Urine Bilirubin (qual)	X		X
	Urine HGB (qual)	X		X
	Urine leukocyte esterase (qual)	X		X
	Urine pH	X		X
Urine sediment	Only positive findings will be reported (for instance, the			
(microscopic	presence of sediment bacteria, casts in sediment, squamous			
examination if	epithelial cells, erythrocytes, leukocytes)			
erythrocytes,				
leukocytes nitrite or				
protein are abnormal				
in urine)				

A: parameters to be determined at Visit 1 (screening examination)

B: parameters to be determined on Day 1 of each period (for time points refer to Flow Chart)

C: parameters to be determined at Visit 5 (end of trial examination)

The tests listed in Table 5.2.3: 2 are exclusionary laboratory tests that may be repeated as required. The results will not be entered in the CRF/database and will not be reported in the CTR. Except for pregnancy tests and drug screening, it is planned to perform these tests during screening only. Pregnancy testing will be performed at screening, prior to run-in, prior to each treatment period, and as part of the end of trial examination. Drug screening will be performed at screening and on day 20 of each treatment period.

Boehringer Ingelheim BI Trial No.: 1402-0019

Proprietary confidential information © 2023 Boehringer Ingelheim International GmbH or one or more of its affiliated companies

Table 5.2.3: 2 Exclusionary laboratory tests

Functional lab group	Test name
Drug screening (urine)	Amphetamine/MDA
	Barbiturates
	Benzodiazepine
	THC
	Cocaine
	Methadone
	Methamphetamines/MDMA/Ecstasy
	Morphine (MOP)
	Phencyclidine
	Tricyclic antidepressants
Cotinine test (urine)	Cotinine (metabolite of nicotine) in urine
Infectious serology (blood)	Hepatitis B surface antigen (qualitative)

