### 7.2.5 Safety analyses

Safety will be analysed based on the assessments described in Section 2.2.2.3. All treated subjects (TS, refer to Section 7.2) will be included in the safety analysis. Safety analyses will be descriptive in nature and based on BI standards. No hypothesis testing is planned.

Boehringer Ingelheim BI Trial No.: 1402-0019

c41232811-04 Trial Protocol Page 61 of 84

19 Oct 2023

Proprietary confidential information © 2023 Boehringer Ingelheim International GmbH or one or more of its affiliated companies

For all analyses, the treatment actually administered (= treatment at onset) to the subject will be used (any deviations from the assigned treatment will be discussed in the minutes of the Report Planning Meeting).

Treatments will be compared in a descriptive way. Tabulations of frequencies/proportions will be used to evaluate categorical (qualitative) data, and tabulations of descriptive statistics will be used to analyse continuous (quantitative) data.

Measurements (such as ECG, vital signs, or laboratory parameters) or AEs will be assigned to treatments (see Section 4.1) based on the actual treatment at the time of the measurement or on the recorded time of AE onset (concept of treatment emergent AEs). Therefore, measurements performed or AEs recorded prior to first intake of trial medication will be assigned to the screening period. Those occurring in the run-in period will be assigned to the run-in period, while all others -from first trial medication intake in respective treatment period to end of REP (see Section 1.2.3) will be assigned to the respective treatment period. Events occurring after the REP but prior to end of study examination date will be assigned to follow-up'. In case of two or more treatments, the follow-up will be summarized according to the previous treatment. These assignments including the corresponding time intervals will be defined in detail in the TSAP. Note that AEs occurring after the last per protocol contact but entered before final database lock will be reported to Pharmacovigilance only and will not be captured in the trial database.

Additionally, further treatment intervals (analysing treatments) may be defined in the TSAP in order to provide summary statistics for time intervals, such as combined treatments, ontreatment totals, or periods without treatment effects (such as screening and follow-up intervals).

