4. CHANGES IN THE PLANNED ANALYSIS OF THE STUDY

This trial has been prematurely terminated during the run-in period as Boehringer Ingelheim decided not to continue with trial execution due to strategic reasons. None of the subjects has started with treatment period 1. Therefore, not all analyses as planned in the CTP will be performed. For all study endpoints listings will be provided. Tables will only be provided for adverse events (AEs). For variables regarding disposition, demography, medical history, concomitant medication and non-drug procedures, exposition, protocol deviations, laboratory data, vital signs and C-SSRS suicidality, only listings will be provided and no descriptive analysis will be carried out. An additional analysis set, the Entered set, will be defined as a base for the disposition listings.

The descriptive and model-based analysis of pharmacokinetic endpoints will not be performed as well, in line with the CTP no PK samples were collected in the run-in period.

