Overall, the REP of 17 days will be considered for evaluation of adverse events in the trial.

The study was prematurely terminated after run-in period. Therefore, the subjects received combined oral contraceptives (COC), but none of the subjects was treated with BI 1358894. Consequently, the REP of ethinylestradiol and drospirenone was 9 days.

Based on this, the following study phases will be defined for the analysis of AEs:

- **Screening**
 - Ranging from 0:00h on day of informed consent until time of first administration of COC.
- **On treatment (labelled “COC (run-in)”)**
 - Ranging from the time of first administration of COC until last administration of COC plus 9 days (216 h) thereafter OR until trial termination (0:00 h on the day after trial termination), whatever occurs first.
- **Follow-up (labelled “Follow-up (run-in)”)**
 - Ranging from the end of REP until trial termination (0:00 h on the day after trial termination).

Section 7.2.5 of the CTP:

Note that AEs occurring after the last per protocol contact but entered before database lock will be reported to Pharmacovigilance only and will not be captured in the trial database.

The following AE displays will be provided in the report:

- In Section 15.3 and Appendix 16.1.13.1.8 (for ClinicalTrials.gov only) of the CTR displays, the on treatment phase will be analysed (labelled with the short label of the study treatment). The screening and follow-up phases will not be included in this analysis.
- In Section 15.4 and Appendix 16.2 (Listings) of the CTR displays, the screening period, as well as the follow-up phases will additionally be included and no totals will be provided.

For detailed information on the handling of the treatments refer to Technical TSAP ADS (analysis data set) plan and Analysis Data Reviewers guide.

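### Does the repeat-measurement rule in SAP 6.7 turn unscheduled values taken on the contraceptive into screening values?

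*SAP*

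**What the plan says.** SAP 6.7 assumes that an unscheduled laboratory or vital-sign value repeats the latest scheduled one, for example to follow up or confirm a result. It then states that "unscheduled measurements will be assigned to the planned time point of the previous scheduled measurement". The rule makes no exception for values taken after first dosing. The same section defines baseline as the last measurement before the first contraceptive (COC) intake.

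Protocol 7.2.5 assigns measurements to treatments "based on the actual treatment at the time of the measurement". Values before first intake belong to screening. For the run-in the rule is: "Those occurring in the run-in period will be assigned to the run-in period". What falls after the residual effect period but before the end-of-study (EoS) examination is follow-up. The protocol leaves the detailed intervals to the SAP.

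SAP 6.1 supplies time-based phases, but only for adverse events: "the following study phases will be defined for the analysis of AEs". SAP 4 reports how far the trial got: "None of the subjects has started with treatment period 1". It does not list the assignment of measurements among the changes to the planned analysis.

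On the schedule, the legend to Protocol Table 5.2.3: 1 reads "B: parameters to be determined on Day 1 of each period", with panel A at screening and panel C at the end-of-trial examination. In the Flow Chart, the run-in row "Self-administration of COC" has one laboratory entry, pointing to footnote 8: "Urine pregnancy test. Additional urine drug screening on day 20 of each period".

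**The concern.** The repeat rule suits a trial with regular scheduled visits, where the previous scheduled value is usually recent and taken under the same treatment. Here the trial ended before the first in-period visit, and the SAP, written with that knowledge, kept the rule unchanged. A liver test drawn because of symptoms in the third week of tablets would be treated as a repeat of the screening panel, although it is a new observation on the contraceptive.

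SAP 7 sorts the listings by subject and visit, and SAP 7.8.2 and 7.8.3 present laboratory and vital-sign data in listings only. A reader could therefore take an on-treatment value for a pre-treatment one in the only output that shows it. The protocol assigns such a value to the run-in period, the SAP does not repeat that rule for measurements, and SAP 4 declares no departure from it. If baseline or adverse-event phase also followed the visit label, the safety account of the run-in would be distorted.

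**Working it through.** No figure in the plan needs reproducing. The check is a trace of the rules, with a little arithmetic on the schedule.

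**1. Scheduled time points left (Flow Chart; Protocol Table 5.2.3: 1).**
- Safety panels: A at screening, B on Day 1 of each of two periods, C at EoS, so 1 + 2 + 1 = 4. Without Periods 1 and 2: 4 − 2 = 2.
- Vital signs: screening, Days 20 and 22 of each period, EoS, so 1 + 4 + 1 = 6. Without the in-period ones: 6 − 4 = 2.
- The run-in pregnancy test is done 1 to 7 days before the run-in starts (Protocol 4.1.4). Its result is not entered in the database (Protocol 5.2.3), so it cannot serve as the previous scheduled record.

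**2. Applying SAP 6.7.** For any unscheduled value between first COC intake and EoS, the previous scheduled measurement is screening. Values before first intake, and repeats after EoS, are placed correctly.

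**3. Length of the window (Protocol 3.1; SAP 6.1).** Tablets run from Day −56 or Day −28 to Day −8, so first to last dose spans −8 − (−56) = 48 days or −8 − (−28) = 20 days. Adding the 9-day residual effect period gives 57 or 29 days for a completed run-in, and less if it was cut short. With screening allowed from Day −91, the widest gap between the screening visit and the last planned tablet is −8 − (−91) = 83 days. That is a design extreme, counted from a Day 1 that no subject reached.

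**4. The two rules side by side.**

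| | SAP 6.7 | Protocol 7.2.5 |
|---|---|---|
| What is assigned | planned time point | treatment or period |
| Value before first COC intake | screening | screening |
| Value after first COC intake, within 9 days of last tablet | screening visit, as a repeat | run-in |
| Value more than 9 days after last tablet, before EoS | screening visit, as a repeat | follow-up |

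The entries differ in the last two rows, but they fill different fields. A record with a screening-repeat visit and a run-in treatment satisfies both rules.

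**5. What a visit label could change.**
- Baseline: nothing. It is set by time relative to first COC intake.
- Change from baseline for vital signs: nothing. It is the value minus baseline, and neither term depends on the label.
- Reference-range flags (SAP 7.8.2): nothing. They depend on the value.
- Adverse events, including the liver events of special interest: nothing. Phases in SAP 6.1 run by clock time from first to last COC intake plus 216 h (9 × 24 h).
- Tables: nothing. SAP 4 plans tables for adverse events only.
- Listings: the visit under which the record is sorted.

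**The case for a change.** The best argument for a change is that it would be cheap and that the protocol asked for it. Protocol 7.2.5 leaves the detailed assignment of measurements to the SAP, and the SAP provides it for adverse events alone. SAP 6.7 is the only visible allocation rule for laboratory and vital-sign values. Unscheduled tests are foreseen: the liver-injury text quoted in SAP 7.8.1 allows for an unscheduled blood test. Such a test is not a repeat of screening in any useful sense, and one sentence would say so.

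Part of this stands. The SAP does not restate the protocol's rule for measurements, and the screening time point is a poor label for a value taken on the contraceptive.

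It does not amount to a contradiction. SAP 3 states that the plan is based on Protocol Section 7, and nothing in SAP 4 withdraws the assignment by treatment, so an analyst would still apply it. SAP 6.1 and 7 refer data handling and listing format to further documents that are not available here. It cannot be concluded that the listings omit the date, time or treatment phase.

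The obvious one-line remedy also has a flaw. Listing every unscheduled value after first dosing under the run-in would mislabel those taken after the residual effect period, which Protocol 7.2.5 sends to follow-up.

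**Conclusion.** No change follows. The trace is correct: under SAP 6.7, an unscheduled laboratory or vital-sign value between first COC intake and EoS takes the screening time point. The consequence is limited to a visit label in listings for the 28 subjects treated in the run-in. The number of such values is not given, and zero is possible. No table, estimate, baseline, adverse-event phase or safety action depends on the label.

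This rests on two readings. The first is that Protocol 7.2.5 still governs the treatment assignment of measurements, as SAP 3 implies. The second is that findings judged clinically relevant are reported as adverse events, as SAP 7.8.2 and 7.8.3 require. A programmer who keeps planned visit and treatment phase as separate fields, with phase set by actual date and time, meets both documents as they stand.

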7. PLANNED ANALYSIS

Safety analysis (refer to [Section 7.8](#)) will be performed by [REDACTED] and will be presented in Sections 15.3 and 15.4 of the CTR and in Appendix 16.2 and 16.1.13.1.

The study was prematurely terminated after run-in period. Therefore, in 15.3 and 15.4 only AEs will be presented. In addition, no descriptive data analysis of PK endpoints and concentrations will be performed.

The format of the listings and tables will follow the BI standards (see “Standards for Reporting of Clinical Trials and Project Summaries” [\(6\)](#)).

The individual values of all subjects will be listed, sorted by subject number and visit. The listings will be included in Appendix 16.2 of the CTR.

Units of variables should be given in the titles or column/row descriptors in brackets (e.g. (mg)).

7.1 DEMOGRAPHIC AND OTHER BASELINE CHARACTERISTICS

Only listings are planned for this section of the report, based on the TS.

7.2 CONCOMITANT DISEASES AND MEDICATION

Only listings are planned for this section of the report, based on the TS.

Concomitant diseases and non-drug therapies will be coded according to the version defined in the decision log [\(4\)](#) of the coding system of the Medical Dictionary for Drug Regulatory Activities (MedDRA). Concomitant medications will be coded according to the most recent version of the World Health Organization Drug Dictionary (WHO-DD). The coding version number will be displayed as a footnote in the respective output.

Section 7.2.5 of the CTP:

Previous and concomitant therapies will be presented without consideration of time intervals and treatment periods.

The diagnoses and medications will be listed. Subjects without any concomitant diagnoses or concomitant therapies will be marked with a “No” in the respective column.

